**d. Withdrawal of individual subjects**

Subjects can leave the study at any time for any reason if they wish to do so without any consequences. The investigator can decide to withdraw a subject from the study for urgent medical reasons.

**e. Specific criteria for withdrawal (if applicable)**

**f. Replacement of individual subjects after withdrawal**

In our power calculation, we anticipated for 20% dropout. If data collection is still in progress, new subjects will be recruited.

**g. Follow-up of subjects withdrawn from treatment**

There will be no follow up on withdrawn subjects.

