#### ii. Secondary study parameters/endpoints (if applicable)

Quality of recovery measured with the quality of recovery questionnaire-15 (QoR-15) (16, 24) at post discharge day at post discharge day 1, 4 and 7.

Postoperative Pain: Experienced postoperative pain (POP) measured with (in-app) NRS for Pain (25) (combined with 11 faces scale) measured at day 1, 4 and 7 post discharge.

Post discharge nausea and vomiting: Experienced post discharge nausea and vomiting (PDNV) measured with the Myles' PDNV assessment scale (21) between intervention and non-intervention group. Measured at day 1, 4 and 7 post discharge.

Medication Dosage and Use: the total dosage of administered analgesics will be assessed during hospital stay and recorded in the medical record. The total dosage of administered analgesics at home after discharge will be assessed by asking patients to indicate which pain medication they have been using. Measured at day 1, 4 and 7 post discharge.

The number of contacts with the hospital, general practitioner or emergency department. All types of contacts (e.g. physically, e-mail, telephone) will be assessed by reviewing the PDMS for registered contacts and by asking the patients to indicate the number of contacts.

Measured at day 1, 4 and 7 post discharge.

The number of surgical complications assessed according to the Clavien Dindo classification of surgical complications (26, 27) will be assessed by reviewing the PDMS and by asking the patients to indicate the number of complications. Measured at day 1, 4 and 7 post discharge.

The number of readmissions. A readmission is defined as an admission to hospital or emergency department for medical care or observation regarding their surgical intervention. Readmissions will be assessed by reviewing the PDMS and by asking the patient to indicate the number of readmissions. Measured at day 1, 4 and 7 post discharge.

Satisfaction: Patients' satisfaction with the provided care will be assessed using a 1-item self-created VAS scale ('not at all to very much', 0-10 range). Satisfaction will be measured at day 1, 4 and 7 post discharge.

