### b. AEs, SAEs and SUSARs

#### i. Adverse events (AEs)

Adverse events are defined as any undesirable experience occurring to a subject during the study, whether or not considered related to the investigational intervention. All adverse events reported spontaneously by the subject or observed by the investigator or his staff will be recorded.

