**d. Follow-up of adverse events**

All AEs will be followed until they have abated, or until a stable situation has been reached. Depending on the event, follow up may require additional tests or medical procedures as indicated, and/or referral to the general physician or a medical specialist. SAEs need to be reported until end of study within the Netherlands, as defined in the protocol

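### Section 7g ends follow-up at withdrawal, section 8d requires every adverse event to be followed until abated or stable, and the plan does not say which rule governs a patient withdrawn for a medical reason

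*Combined protocol and SAP*

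**What the plan says.** Five parts of the combined protocol and SAP bear on this.

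- Section 7d (withdrawal) lets patients leave at any time and adds: "The investigator can decide to withdraw a subject from the study for urgent medical reasons".
- Section 7g, headed "Follow-up of subjects withdrawn from treatment", consists of one sentence: "There will be no follow up on withdrawn subjects".
- Section 8d (follow-up of adverse events) states "All AEs will be followed until they have abated, or until a stable situation has been reached". It adds that "follow up may require additional tests or medical procedures as indicated, and/or referral to the general physician or a medical specialist", and that "SAEs need to be reported until end of study within the Netherlands, as defined in the protocol".
- Section 7a.ii plans to collect contacts, surgical complications and readmissions from the patient data management system (PDMS) and from patients themselves. For readmissions: "Readmissions will be assessed by reviewing the PDMS and by asking the patient to indicate the number of readmissions".
- Section 9 analyses patients in the arm to which they were randomised. It excludes only those lost through withdrawn consent or cancelled surgery. Section 9d handles missing data by multiple imputation.

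**The concern.** Sections 7g and 8d give a site opposite instructions for a patient who is withdrawn while an AE is unresolved. Sites may settle this differently, and nothing in the plan would show which rule each had used.

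The data at stake are the later course of the event and anything that follows it. Complications and readmissions are between-arm comparisons in the secondary objectives (section 2c), and hospitalisation is also an SAE criterion (section 8b.ii). If collection stops because of a medical event, the missing data depend on the outcome being measured. The trial is unblinded, and only the app arm has daily symptom reporting with staff triage (section 4a). Events that prompt withdrawal could therefore come to light at different rates in the two arms. That is a possibility, not something the documents show.

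**Working it through.** The point rests on comparing sections. The only related figure in the plan is the dropout margin, which comes last.

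**1. Scope of each rule.** The 7g heading refers to withdrawal from treatment, but its sentence covers every withdrawn subject. Section 8d covers all AEs. Section 8b.i defines an AE as "any undesirable experience occurring to a subject during the study, whether or not considered related to the investigational intervention", so a medical reason urgent enough for withdrawal would naturally be one. That step is an inference: section 7d does not define the reasons, and section 7e (specific withdrawal criteria) has no text under its heading.

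**2. Applying both rules to one patient.** Take a patient withdrawn under 7d with an unresolved AE. Under 7g, follow-up stops. Under 8d, it continues until the event abates or stabilises. Section 8d also runs SAE reporting to end of study, which section 11e ties to the final follow-up of the last patient and not to an individual's exit. Both rules cannot be met.

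**3. Is there a reconciling statement?** Sections 8b.i and 8b.ii require AEs to be recorded and SAEs to be reported, without exempting withdrawn patients. Nothing confines 7g to questionnaires, separates stopping the app from leaving the study, or says which section prevails.

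**4. What is kept and what may be lost if 7g is applied.**
- Kept: the event that led to withdrawal, because 8b.i and 8b.ii require it to be recorded or reported when it becomes known.
- May be lost: its course and outcome, and any later complication, readmission or SAE.
- Unstated: whether the PDMS review in 7a.ii continues after withdrawal.

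**5. Consequence for the analysis.** Section 9 does not list investigator withdrawal among its exclusions, so the patient stays in the intention-to-treat set. Any outcome not collected would fall to imputation under 9d, with missingness linked to the medical event. Section 7f also foresees recruiting new subjects while data collection is in progress.

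**6. Size.** The plan's sample size reproduces. With a difference of 8.0, SD 19.1, two-sided alpha 0.05 and 80% power:

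n per group = 2 × (1.960 + 0.842)² × 19.1² / 8.0² ≈ 89.5, so 90 by the normal approximation.

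Exact t-test power is 79.8% at 90 and 80.2% at 91, which confirms the stated 91 per group. The total is 2 × 91 = 182, and 182 / (1 − 0.20) = 227.5, so 228, close to the planned 230. The margin is 230 − 182 = 48 patients (20% of 230 is 46). Section d of the study population part sets this margin for all dropout and incomplete data. It is not split by reason, so the number withdrawn for medical reasons cannot be derived from it.

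**The case against.** The strongest reply is that the two sections have different subjects. Section 7g sits in Methods and can be read as covering study assessments, while 8d is the dedicated section on AE follow-up and would govern events. This reading is plausible, and under it nothing is lost from AE follow-up. But the text does not state it: the 7g sentence is unqualified, and a site could fairly apply it to everything.

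A second reply is that few patients may be affected. The intervention is monitoring on top of routine care, section 8b.ii expects no AEs from it, and failure of same-day discharge is dealt with separately in the exclusion criteria. This stands as a limit on size. It does not remove the conflict.

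Three stronger readings are tempting, and the documents do not support them.

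- *That the patient disappears from the safety data during the event.* The event itself is recorded under 8b. Only what comes afterwards is at risk, and only if 7g prevails.
- *That later readmissions and complications will go uncounted.* Section 7g does not expressly stop the PDMS review, which needs no contact with the patient. The plan is silent on whether it continues.
- *That a large share of readmissions would be lost.* Any such share comes from assumed inputs. Suppose half of medically withdrawn patients are readmitted, always after withdrawal, and 2% of the rest are readmitted. Ten withdrawals then lose 5 of 5 + 220 × 0.02 = 9.4 (53%). Three lose 1.5 of 1.5 + 227 × 0.02 = 6.04 (25%). One loses 0.5 of 0.5 + 229 × 0.02 = 5.08 (10%). None loses nothing. None of these inputs is in the documents, so the range shows only that the answer follows the assumption. A readmission that was itself the reason for withdrawal would already be known.

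**Conclusion.** The conflict between 7g and 8d is real: both are unqualified, neither is given precedence, and 7d makes the situation foreseeable. The loss of data is conditional. It arises if a site applies 7g as written, and it concerns the later course of the event and later complications, readmissions and SAEs in patients whom section 9 keeps in the analysis. The number of patients cannot be derived. The sample size is unaffected.

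The conclusion assumes that at least some withdrawals for urgent medical reasons happen with an AE unresolved. It does not depend on the arms differing. Confidence is high on the inconsistency and limited on how much data would be lost. It should be corrected because the missing data would depend on the outcome and can be avoided cheaply.

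**What to change.** Reconcile sections 7d, 7g and 8d so that a site has one instruction for a patient withdrawn with an ongoing event. How AEs are then followed clinically is for the sponsor to settle.

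For data collection:

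- Limit no follow-up in 7g to patients who withdraw consent to further use of their data.
- For all other withdrawn patients, state that the PDMS review in 7a.ii (contacts, complications, readmissions) continues to day 7.
- State that events found in this way are counted in the arm as randomised, in line with section 9.

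The cost is a wording change and a few extra record checks, since the review is already planned. One limit remains: section 7a.ii also relies on patients' own reports, and for a withdrawn patient who no longer answers, that part would still be missing.

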**h. Premature termination of the study**

Not applicable

## 8. SAFETY REPORTING

### a. Temporary halt for reasons of subject safety

In accordance to section 10, subsection 4, of the WMO (30), the sponsor will suspend the study if there is sufficient ground that continuation of the study will jeopardise subject health or safety. The sponsor will notify the accredited METC without undue delay of a temporary halt including the reason for such an action. The study will be suspended pending a further positive decision by the accredited METC. The investigator will take care that all subjects are kept informed.

### b. AEs, SAEs and SUSARs

#### i. Adverse events (AEs)

Adverse events are defined as any undesirable experience occurring to a subject during the study, whether or not considered related to the investigational intervention. All adverse events reported spontaneously by the subject or observed by the investigator or his staff will be recorded.

#### ii. Serious adverse events (SAEs)

A serious adverse event is any untoward medical occurrence or effect that

- results in death;
- is life threatening (at the time of the event);
- requires hospitalisation or prolongation of existing inpatients' hospitalisation;
- results in persistent or significant disability or incapacity;
- is a congenital anomaly or birth defect; or
- any other important medical event that did not result in any of the outcomes listed above due to medical or surgical intervention but could have been based upon appropriate judgement by the investigator.

An elective hospital admission will not be considered as a serious adverse event.

The investigator will report all SAEs to the sponsor without undue delay after obtaining knowledge of the events, except for the following SAEs: The sponsor will report the SAEs through the web portal *ToetsingOnline* to the accredited METC that approved the protocol, within 7 days of first knowledge for SAEs that result in death or are life threatening followed by a period of maximum of 8 days to complete the initial preliminary report. All other SAEs will be reported within a period of maximum 15 days after the sponsor has first knowledge of the serious adverse events.

Seen the nature of our intervention, i.e. remote monitoring on top of routine postoperative care, no adverse or serious adverse events are expected.

**iii. Suspected unexpected serious adverse reactions (SUSARs)**

Not applicable.

**c. Annual safety report**

Not applicable.

**d. Follow-up of adverse events**

All AEs will be followed until they have abated, or until a stable situation has been reached. Depending on the event, follow up may require additional tests or medical procedures as indicated, and/or referral to the general physician or a medical specialist. SAEs need to be reported until end of study within the Netherlands, as defined in the protocol

**e. [Data Safety Monitoring Board (DSMB) / Safety Committee]**

Not applicable

## 9. STATISTICAL ANALYSIS

All statistical analyses will be conducted according to the intention-to-treat principle (31, 32) considering all patients in the treatment groups to which they were randomly assigned, excluding cases lost to follow-up due to withdrawal of consent or cancellation of surgery. Continuous distribution of the data will be assessed by visual inspection of histograms and normality tests. For both study arms, the baseline characteristics will be reported for the intervention and control group and expressed as counts and percentages, means and standard deviations (SD), or medians and interquartile ranges (IQR) whenever appropriate. Baseline characteristics of patients with and without complete follow up will be compared to examine whether selective dropout occurred. Analyses will be performed using IBM SPSS Statistics for Windows, Version 22.0. Armonk, NY: IBM Corp.

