### 3. STUDY DESIGN

A two-arm multicenter non-blinded randomized controlled trial with mixed methods design will be conducted at the day care nursing wards of OLVG Hospital (Locations Oosterpark and Jan Tooropstraat), Amsterdam, the Netherlands, Canisius Wilhelmina Hospital, Nijmegen, the Netherlands and Maasstad Hospital, Rotterdam, the Netherlands. Surgical specialisms involved are gynecology, eye-nose and throat, oral and maxillofacial, orthopedics, general and vascular, trauma and urology. Surgical day care patients will be randomly assigned to one of the two study arms, remote monitoring with a smartphone application (intervention) or standard of care (no remote monitoring) after hospital discharge. Study period is expected to run from 1st of February 2022 up to the 31st December 2022.

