##### **c. Exclusion criteria**

A potential subject who meets any of the following criteria will be excluded from participation in this study:

- Not able to speak or understand the Dutch language
- Mentally impaired (e.g. dementia, retardation)

During study:

- Patients who experience a unexpected post-operative complication or prolonged recovery with the result that discharge on the same day of the surgical intervention is not possible will be excluded

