### **c. Study procedures**

Patients are recruited to participate in this study during their appointment for anaesthesia pre-assessment (e.g. online assessment, telephone assessment or during visiting the anaesthesia outpatient department). An anaesthesiologist, trainee nurse specialist, physician assistant or medical assistant will verbally explain the study. If interested, they receive an information-letter about the study, and an informed consent form (PIF\_IC\_e1\_e2\_QuReMo\_Versie1\_14\_7\_2021).

Patients who are not informed during the preoperative assessment will be contacted afterwards by one of the researchers to explain the study and to ask them to consider participation. If interested, they receive an information-letter about the study, and an informed consent form (PIF\_IC\_e1\_e2\_QuReMo\_Versie1\_14\_7\_2021).

The patients are given a reflection period of at least 48 hours, after that a researcher or medical assistant will contact the patient if they agree to participate. Patients who have been asked to participate are earmarked in the PDMS (e.g. EPIC). A patient who wishes to participate is asked to sign the consent form and bring it on the day of admission. Patients who, forget to bring their consent form are provided a copy, which is then to be signed on the day of admission. Accordingly, both researchers and patients receive a wet ink copy of the consent form.

After receiving informed consent, the researchers will record the baseline characteristics to the Castor EDC database and perform the randomisation procedure. Moreover, no data is recorded that could trace back the identity of the patients. By randomizing, an anonymous study identification number is allocated to the patients. The researchers from the participating hospitals will keep a secured database in which patient hospital number corresponds with the study identification number, stored locally at their own hospital server. Two days before admission patients in the remote monitoring group (intervention group) receive an invitation e-mail from Luscii © sent by a medical assistant from the anaesthesia outpatient department with instructions to download and install the remote monitoring application. Perioperative patients from both the intervention group and the standard of care group receive anaesthesia

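### The analysis is called intention-to-treat, yet consent withdrawals are dropped as cases, all withdrawn subjects lose follow-up, and one post-randomisation exclusion is not listed

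*Combined protocol and SAP*

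**What the plan says.** Section 9 (opening paragraph) commits to intention-to-treat, "considering all patients in the treatment groups to which they were randomly assigned", and continues in the same sentence: "excluding cases lost to follow-up due to withdrawal of consent or cancellation of surgery". Those are the only two exclusions it names.

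Section 9.a plans a day-by-day t-test or Mann-Whitney test and a mixed model with a random intercept, using QoR-15 before surgery and on days 1, 4 and 7. Section 9.d plans multiple imputation for missing data, without saying whether withdrawn patients are among those imputed.

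The exclusion criteria (Study population, c) add a rule that operates during the study: patients with a complication or slow recovery "with the result that discharge on the same day of the surgical intervention is not possible will be excluded". The trial is open-label (Section 3: "A two-arm multicenter non-blinded randomized controlled trial with mixed methods design"), and under Section 7.c the arm is known before surgery: "Two days before admission patients in the remote monitoring group (intervention group) receive an invitation e-mail from Luscii".

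Section 7.d gives two ways out of the study. The patient may go ("Subjects can leave the study at any time for any reason"), or the investigator may withdraw the patient for urgent medical reasons. Section 7.g, headed "Follow-up of subjects withdrawn from treatment", then says: "There will be no follow up on withdrawn subjects".

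**The concern.** An intention-to-treat analysis keeps randomised patients and uses what was observed on them. Here the label and the rule differ in three places.

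1. Removing consent withdrawals as cases discards scores already given. A patient who leaves after day 4 may have supplied three of the four planned QoR-15 scores. The mixed model and the imputation could use them; the stated exclusion takes them away.
2. A patient withdrawn by the investigator has not withdrawn consent, yet Section 7.g stops the questionnaires. The reason for leaving is medical, so the missing day-7 score is likely to be related to recovery.
3. The same-day-discharge exclusion falls after randomisation and is absent from the list in Section 9, so a reader of that section would think the analysed set is wider than it is.

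At stake is the comparability of the arms. The trial is unblinded and the outcome is self-reported, so losses after discharge can depend on arm and on recovery. Replacing withdrawn subjects (Section 7.f) restores numbers but not the outcomes of those who left.

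**Working it through.** **The plan's own figure.** Inputs from the sample size section: difference 8.0, SD 19.1, two-sided alpha 0.05, power 80%.

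- Normal approximation: n = 2 × (1.960 + 0.842)² × (19.1/8.0)² = 2 × 7.85 × 5.70 = 89.5, so 90 per arm.
- Exact noncentral t: 90.45, so 91 per arm, with power 0.802. The stated 91 reproduces.
- For 20% loss: 91/0.8 = 113.75, so 114 per arm or 228, consistent with the stated 230.
- With 115 per arm (equal allocation, inferred from two groups of 91 and blocks of four), 20% loss leaves 92 per arm and power 0.807.

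Precision is therefore protected. The question is bias and the definition of the set.

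**The rules side by side.**

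- Consent withdrawal: Section 9 removes the case. Section 9.d would impute missing data but does not say whether these patients are covered.
- Cancelled surgery: Section 9 removes the case. This is not contested.
- No same-day discharge: excluded by the eligibility section, not named in Section 9.
- Investigator withdrawal: allowed by 7.d, follow-up ended by 7.g, not named in Section 9. These patients stay in the set without a day-7 score.

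**Illustration of what keeping earlier scores would achieve.** Only the SD of 19.1 comes from the plan. Assumed: no true effect, the same SD at every visit, equal correlation ρ of 0.3 to 0.7 between visits, withdrawal after day 4, lower scorers more likely to leave, and a correlation of 0.5 in strength between withdrawal tendency and the score. Withdrawal shares are 10% vs 5%, or 15% vs 5%.

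For a share p, the upward shift in the mean of those who remain, per unit SD and unit correlation, is m(p) = φ(z_p)/(1 − p), where z_p is the normal quantile at 1 − p: m(0.05) = 0.1086, m(0.10) = 0.1950, m(0.15) = 0.2743.

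D = 19.1 × 0.5 × [m(p₁) − m(p₂)]:

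- 10% vs 5%: 9.55 × 0.0864 = 0.83 points
- 15% vs 5%: 9.55 × 0.1657 = 1.58 points
- 10% vs 10%: 0

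*Withdrawal driven by the day-4 score.* Excluding the cases biases the day-7 difference by ρ × D:

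| ρ | 10% vs 5% | 15% vs 5% |
|---|---|---|
| 0.3 | 0.25 | 0.47 |
| 0.5 | 0.41 | 0.79 |
| 0.7 | 0.58 | 1.11 |

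Using the three earlier scores in a random-intercept model leaves 0.

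*Withdrawal driven by the unseen day-7 score.* Excluding the cases gives bias D. Using the three earlier scores removes the share 3ρ²/(1 + 2ρ):

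| ρ | Share removed | Left, 10% vs 5% | Left, 15% vs 5% |
|---|---|---|---|
| 0.3 | 0.27/1.6 = 16.9% | 0.69 | 1.32 |
| 0.5 | 0.75/2.0 = 37.5% | 0.52 | 0.99 |
| 0.7 | 1.47/2.4 = 61.2% | 0.32 | 0.61 |

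A simulation with 4 million patients per arm agreed within about 0.03. Reversing the shares reverses the sign. If only the pre-surgery score exists, the share removed falls to ρ², that is 9% to 49%. No size can be put on the investigator withdrawals or the same-day-discharge exclusion.

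**The case against.** Much of the opposing case has force.

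- Excluding cases is itself a rule, so the plan is not silent on consent withdrawals. That stands. The objection is to the rule, on its natural reading. What happens to data after withdrawal may also be settled in the consent form or the data management plan, which are not in the supplied text; the fix is therefore conditional on consent.
- A reader might take the 20% allowance, 230 − 182 = 48 patients, as the size of the excluded group. The documents do not support that. The allowance covers all dropout and incomplete data, whereas Section 9 excludes only consent withdrawals and cancelled surgery. Nor does the expectation of few losses in Section 9.d show otherwise: a cautious allowance can sit beside it.
- A reader might infer that the same-day-discharge exclusion biases the comparison. It would do so only if knowing the arm affected discharge, and nothing in the documents shows that. It is decided before app recording at home begins, and the endpoints are timed from discharge. An analyst who reads both sections would apply it. What remains is mainly a labelling gap.
- A reader might infer that patients who merely stop using the app lose follow-up. Only the heading of Section 7.g suggests this. Section 7.d speaks of leaving the study, and Section 7.c sends the questionnaire to both groups. One clarifying sentence is enough.
- Safeguards exist: telephone contact with non-responders in both arms (7.c), a baseline comparison of patients with and without complete follow-up (9), and a sensitivity analysis if the mixed model indicates bias (9.a). They limit the problem. However, the first does not reach withdrawn subjects, the second describes selective dropout without correcting it, and the third is conditional with no stated criterion.

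**Conclusion.** The point holds as a modest, inexpensive correction that should be made. The set to be analysed is not the full intention-to-treat set claimed; usable scores from consent withdrawals are, on the natural reading, discarded; and patients withdrawn by the investigator lose their day-7 outcome although they have not withdrawn consent.

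The size and direction of any bias cannot be derived from the documents. In the assumed scenarios it is at most about 1.6 points, one fifth of the 8.0-point target (1.58/8.0 = 20%), and zero with equal shares and equal selection. That is the largest of the scenarios examined, not a bound; the withdrawal shares, the correlations and the timing are all assumptions. Keeping earlier scores removes all of the bias when withdrawal depends on the observed day-4 score, but only 17% to 61% when it depends on the unseen day-7 score. The sample size is not in question.

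**What to change.** **Section 9.** Keep patients who withdraw consent in the set as randomised, and use all data collected up to withdrawal, where consent allows, in both the mixed model and the multiple imputation. Add the same-day-discharge exclusion to the listed exclusions, label the resulting set modified intention-to-treat, and report every post-randomisation exclusion, cancelled surgery included, by arm and reason.

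**Section 7.g.** State that withdrawal by the investigator, or stopping use of the app, does not end questionnaire follow-up unless the patient withdraws consent for data.

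**Cost.** Protocol and SAP wording, slightly more data handling, and a few more of the existing questionnaires. The replacement rule in 7.f can stay. Day-7 scores after a true withdrawal of consent will still be missing and rest on model assumptions, so part of any bias can remain.
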